2.2 Secondary Objective(s)

- Concordance between clinical assessment/diagnosis and the localization of Tc 99m tilmanocept by planar and/or SPECT/CT imaging in cutaneous and non-cutaneous sites of KS.
- Qualify and quantify Tc 99m tilmanocept localization intensity on imaging with CD206 locale and quantity by histology and IHC in biopsied KS lesions to determine optimal IV dose.
- Concordance of localization of Tc 99m tilmanocept via IV and SC routes of administration by planar and/or SPECT/CT imaging in cutaneous and non-cutaneous sites of KS.

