5.2 Investigational Product Dosage and Administration

This study includes IV administration of 3 doses Tc 99m tilmanocept: 100 μ g/ 5 mCi, 100 μ g/ 10 mCi, and 200 μ g/ 5 mCi. All subjects will receive IV administration at one of these three doses. Cohort 3 will serve as a comparator arm, and Cohort 3 subjects will additionally receive a SC injection of Tc 99m tilmanocept at the Cohort 3 dose of 200 μ g/ 5 mCi (see Table 1). At least one subject enrolled into each cohort must meet inclusion criteria 4c (suspected non-cutaneous or confirmed non-cutaneous KS), as described in [Section 4.1](#).

Table 1. Dosing Cohorts

	Tc 99m tilmanocept Dose	Route of Administration	Number of Subjects
Cohort 1	100 μ g/ 5 mCi	IV	n = 4
Cohort 2	100 μ g/ 10 mCi	IV	n = 4
Cohort 3	200 μ g/ 5 mCi	IV and SC	n = up to 6

All subjects will receive Tc 99m tilmanocept through an IV route of administration. A single syringe will be used and injected as a slow push into the venous catheter. The preferred site of catheter placement will be the left or right antecubital vein. Injection volume will be 1.0 mL in sterile normal saline. At the completion of the injection, a 10 cc sterile normal saline flush will be administered.

Cohort 3 subjects will also receive Tc 99m tilmanocept through a SC route of administration. Two syringes will be used and injected bilaterally as a slow push into the ankle(s) or the dorsal surface of the foot (feet). Total injection volume will be 1.0 mL (0.5 in each syringe) in sterile normal saline. Each syringe will contain half of the intended total dose of 200 μ g/ 5 mCi (100 μ g/ 2.5 mCi per syringe).

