9.3 Efficacy Variables

The efficacy variables for this study are as follows:

- Nuclear medicine specialist determination of presence/absence of illumination (i.e., localization positive/negative, anatomic site) relative to background from SPECT imaging results for each subject;
- Clinically identified presence/absence of KS (based on any previous diagnostic evaluations);
- Quantitative SPECT gamma counts for each biopsied lesion.

The efficacy endpoints for this study are as follows:

- Per subject localization rate of Tc 99m tilmanocept in at least one KS suspected or confirmed lesion by planar and/or SPECT/CT imaging
- Per lesion/region concordance of Tc 99m localization with anatomical areas of active KS defined by confirmed diagnosis or clinical symptomology
- Localization intensity for each biopsied and clinically defined lesion as determined by quantitative SPECT gamma counts
- Per biopsied lesion proportion of CD206-expressing cells and total CD206 as determined by histology and relative IHC fluorescence
- Per lesion/region concordance of IV vs SC Tc 99m localization with anatomical areas of active KS defined by confirmed diagnosis or clinical symptomology.
- Per subject localization rate of Tc 99m tilmanocept in areas other than KS by planar and/or SPECT/CT imaging

- Per area localization rate of Tc 99m tilmanocept in the most frequently identified areas other than KS by planar and/or SPECT/CT imaging

A localized subject is one for whom Tc 99m by planar and/or SPECT/CT imaging results in the illumination of at least one site relative to background as determined by the nuclear medicine specialist.

A localized KS lesion is a lesion that is both clinically identified or suspected KS and planar or SPECT/CT illuminated.

Localization in areas other than KS will also be defined per subject and per area, where these areas are clinically negative KS locations based on clinical symptomology.

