9.5.3 Analysis of Efficacy Variables

The number and percentage of subjects with at least one biopsy-confirmed or clinically suspected KS lesion that has localized with Tc 99m tilmanocept by planar and/or SPECT/CT imaging will be

computed. A 95% exact confidence interval on the per subject localization rate will be computed. This analysis will be performed by dose.

Per region lesion localization of Tc 99m tilmanocept by planar and/or SPECT/CT imaging will be computed across all biopsy-confirmed or clinically suspected KS lesions of all subjects. A 95% exact confidence interval on per region lesion localization will be calculated. This analysis will be performed by dose.

Localization intensities of biopsied lesions will be summarized by descriptive statistics (mean, median, standard deviation, minimum, maximum and range) for each dose.

Per biopsied lesion proportion of CD206-expressing cells and quantity of CD206 as determined by histology and IHC fluorescence will be summarized by descriptive statistics (mean, median, standard deviation, minimum, maximum and range) for each dose.

Concordance between between IV and SC tilmanocept in biopsy-confirmed or clinically suspected KS lesion sites will be assessed with a cross-tabulation including the joint probability distribution. The site will be the sampling unit for this analysis. An exact version of McNemar's test will be performed, testing the null hypothesis

$$H_0: \pi_{IV} = \pi_{SC}$$

$$H_A: \pi_{IV} \neq \pi_{SC}$$

where π_{IV} and π_{SC} represent the probabilities of localization with IV (only) tilmanocept and localization with SC tilmanocept only respectively.

In addition, descriptive statistics will be generated relative to the concordance and reverse concordance of observed sites of discrete localization of Tc 99m tilmanocept following IV and SC administration.

The number and percentage of subjects with at least one anatomical site other than KS that has been localized with Tc 99m tilmanocept by SPECT imaging will be computed. A 95% exact confidence interval on the per subject localization rate will be computed. This analysis will be performed by dose and overall.

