2.0 Data Analysis Considerations

2.1 Types of Analyses

All results will be based on descriptive statistics. Unless otherwise stated, continuous variables will be summarized via sample size, mean, standard deviation, median, minimum, and maximum. Categorical variables will be summarized via frequency counts and percentages.

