4.2 Analysis of Efficacy Variables

Localization in KS Sites

The number and percentage of subjects with at least one biopsy-confirmed or clinically suspected KS lesion that has localized with Tc 99m tilmanocept by planar and/or SPECT/CT imaging will be computed. A 95% exact confidence interval on the per-subject localization rate will be computed. This analysis will be performed by dose group and route of administration.

Per-lesion/region localization of Tc 99m tilmanocept by planar and/or SPECT/CT imaging will be computed across all biopsy-confirmed or clinically suspected KS lesions of all subjects. A 95% exact confidence interval on the per-lesion/region localization will be calculated. This analysis will be performed by dose group and route of administration.

An analysis table will also be provided to display the counts of KS lesions localized by imaging that were not previously identified clinically.

Concordance between IV and SC tilmanocept in biopsy-confirmed or clinically-suspected KS lesion sites will be assessed with a cross-tabulation of the IV and SC findings, including the joint probability distribution. The sampling unit for this analysis will be the site. An exact conditional version of McNemar's test will be performed to test the hypotheses

$$H_0: \pi_{IV} = \pi_{SC}$$
$$H_A: \pi_{IV} \neq \pi_{SC},$$

where π_{IV} and π_{SC} represent the probabilities of localization with IV (only) tilmanocept and SC (only) tilmanocept, respectively. In addition, the number and proportion of subjects with concordance and reverse concordance of observed sites of discrete localization of Tc 99m tilmanocept following IV and SC localization will be summarized.

Localization Intensity by Planar and/or SPECT/CT Imaging

Tc 99m tilmanocept average pixel intensity and percent above background will be summarized with descriptive statistics (mean, standard deviation, minimum, median, maximum, and range) for each biopsied lesion localized on imaging following IV injection of Tc 99m tilmanocept by dose group. Summary statistics will be presented separately by imaging type (planar, SPECT/CT).

Proportion of CD206-expressing Cells

Per biopsied-lesion proportion of CD206-expressing cells as determined by histology and IHC fluorescence will be summarized by descriptive statistics (mean, standard deviation, minimum, median, maximum, and range) by dose group.

Localization in Non-KS Sites

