6.3 Subject Imaging

Each subject will undergo whole body planar imaging. SPECT/CT imaging of region(s) of interest is optional for each subject. Results of all imaging procedures will be listed.

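### Objective 2 promises an optimal IV dose, but the plan has no lead measure, no between-dose estimate and no role for CD206, and its table shells omit Cohort 1

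*Protocol*

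**What the plan says.** Protocol 2.2 lists as a secondary objective the relation of localization intensity to CD206 "in biopsied KS lesions to determine optimal IV dose". The Synopsis and SAP 1.0 and 4.1 repeat this aim. Only HHV8 quantification is labelled exploratory.

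Three IV doses are studied: "This study includes IV administration of 3 doses Tc 99m tilmanocept", given to 4, 4 and up to 6 subjects (Protocol 5.2, Table 1).

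The planned analysis of intensity is as follows:

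- Protocol 9.3 names one intensity endpoint: "Localization intensity for each biopsied and clinically defined lesion as determined by quantitative SPECT gamma counts".
- Protocol 9.5.3: "Localization intensities of biopsied lesions will be summarized by descriptive statistics", for each dose.
- SAP 4.2: "Tc 99m tilmanocept average pixel intensity and percent above background will be summarized with descriptive statistics", by dose group, with planar and SPECT/CT presented separately. It covers only biopsied lesions that localized on imaging after IV injection.
- SAP 6.3: "SPECT/CT imaging of region(s) of interest is optional for each subject".
- SAP 2.1: "All results will be based on descriptive statistics".
- SAP Appendix B: the shells of Tables 10 and 11 (intensity) and Table 12 (CD206) have rows for Cohort 2, Cohort 3 and all cohorts combined. None has a Cohort 1 row.

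**The concern.** An objective to determine a dose needs a rule that turns data into a dose, or at least an estimate of how the doses differ. Neither document has one. Some cohort will always have the highest mean on any given measure, and there are four measures to choose from. An optimal dose could therefore be named after seeing which summary favours it, and a reader could not separate a dose effect from selection or from noise in groups of 4 to 6.

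Three further gaps make this worse:

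- The endpoint is SPECT counts, yet SPECT/CT is optional and the SAP summarizes other quantities.
- The objective ties intensity to CD206, but no analysis links the two.
- As tabulated, Cohort 1 cannot be compared with the other doses.

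**Working it through.** **Inputs from the documents.** Cohort sizes are 4, 4 and up to 6, and 4 + 4 + 6 = 14, which reproduces the planned maximum in Protocol 9.4. Each subject has one biopsied lesion, and the footnotes to Tables 10 and 11 put the summaries at subject level. Two intensity variables on two imaging types give 2 × 2 = 4 summaries. Three doses are studied; the shells tabulate two.

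**Assumptions, not in the documents.** Measures are normal with equal variance and a common correlation ρ. All subjects contribute to all measures. The dose with the highest mean is taken as the one named.

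**1. No true difference: chance that the four summaries do not all name the same dose.** For independent summaries and D doses the probability is 1 − D(1/D)⁴. Three doses give 1 − 3/81 = 96.3%; two doses give 1 − 2/16 = 87.5%. Simulation of the cohort means (200,000 draws) gives the correlated cases:

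| ρ | Three doses (4, 4, 6) | Two doses, as in the shells (4, 6) |
|---|---|---|
| 0 | 96% | 88% |
| 0.5 | 75% | 60% |
| 0.7 | 60% | 46% |
| 0.8 | 50% | 37% |
| 0.9 | 37% | 26% |
| 0.95 | 26% | 18% |

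The figure exceeds one half only while ρ is below about 0.80 (three doses) or 0.65 (two doses). If only the two planar summaries exist, it is 67% at ρ = 0, 36% at 0.7 and 21% at 0.9 (three doses).

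**2. One dose truly better.** Let the cohort of 6 be better by an assumed 0.5 SD. A single measure then names another dose 35% of the time, whatever ρ is. At least one of four does so in 82%, 67% and 54% of trials at ρ = 0, 0.5 and 0.8.

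**3. Raw intensity against a ratio to background.** Cohort 2 receives 10 mCi and the other cohorts 5 mCi, a ratio of 2. Suppose true uptake is the same at all doses, pixel counts are proportional to activity, and scan time and relative background are fixed. Raw intensity then names Cohort 2 in about 96% of trials if the between-subject CV is 50%, or 78% if it is 100%. The ratio names Cohort 2 in about a third. The two disagree in 63% or 45% of trials, even though they rest on the same lesion uptake. Protocol 8.3 also allows shorter scans at higher activity, in which case raw intensity would depend on scan time as well.

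**4. Precision of a between-cohort difference.** The 95% half-width is t(0.975, n₁+n₂−2) × √(1/n₁ + 1/n₂) in SD units.

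- 4 vs 4: 2.447 × 0.707 = 1.73 SD.
- 4 vs 6: 2.306 × 0.645 = 1.49 SD.

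**The case against.** The strongest reply is that the four measures come from the same lesion after the same injection, and Data Listing 17 places percent above background beside the pixel and background intensities from which it appears to be calculated. High correlation is therefore plausible. A reader might infer from the 75% figure that chance would make the summaries disagree in most trials. The documents do not support that: they give no correlation, and at 0.9 the figure is 37%. This part of the objection stands. High correlation does not close the gap, though, because a twofold difference in activity can separate raw intensity from a ratio (step 3).

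A reader might also infer an inflated false-positive rate from many dose comparisons. No between-dose test of intensity is planned, so no such rate applies.

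Nor is it right that no measure is named anywhere. Quantitative SPECT counts are the stated endpoint, but neither document makes them decide the dose.

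Two more points stand. The calculations treat the highest mean intensity as optimal, which the documents never say. Non-localized lesions and missing SPECT/CT may leave fewer than 4, 4 and 6 values. Finally, this is a secondary objective in a Phase 1 safety study that is declared descriptive. That limits the severity, but it also conflicts with the word determine.

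**Conclusion.** The concern holds as a mismatch between objective and analysis: the planned summaries cannot support a determination of the optimal IV dose. This follows from the text alone. So do the undefined role of CD206, the difference between the SPECT endpoint and the SAP measures, and the absence of Cohort 1 from the shells. The same omission recurs across Tables 10, 11 and 12, while neighbouring shells include Cohort 1, so it is unlikely to be an artefact of text extraction.

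The size of the chance component is conditional. With no true difference, disagreement among the four measures runs from 75% to 26% of trials as the assumed correlation goes from 0.5 to 0.95, so it could often happen but cannot be called the rule. The 35% wrong-dose figure rests on an assumed 0.5 SD advantage. The change should be made, but it does not affect the primary safety endpoint.

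**What to change.** 1. In Protocol 2.2, the Synopsis, SAP 1.0 and SAP 4.1, replace the optimal-dose clause with: *to describe localization by IV dose; any dose ranking is exploratory*. State how CD206 is to be related to intensity.
2. In SAP 4.2, pre-specify one lead intensity measure and reconcile it with the SPECT-count endpoint. Percent above background on the planar scan is a reasonable candidate, because planar imaging is acquired in every subject and Cohort 2 receives twice the activity. The choice is open to debate; the need to make one is not.
3. State how biopsied lesions that did not localize count in that measure.
4. Report the between-cohort differences in the lead measure with 95% CIs, and label the other intensity and localization summaries supportive.
5. Add Cohort 1 rows to Tables 10, 11 and 12.

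The cost is SAP and objective wording, up to three added estimates and three table rows, with no new data. The downside is a more modest dose claim and wide intervals (half-width about 1.7 SD for 4 vs 4 and 1.5 SD for 4 vs 6). Naming one measure removes selection among measures but does not add power: a two-sided 5% comparison would have 22% (4 vs 4) or 28% (4 vs 6) power for a 1 SD difference. That is why estimates with intervals are proposed and not tests.

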2.3 Exploratory Objective(s)

- Quantify HHV8 in biopsied KS lesions by qPCR

3 OVERVIEW OF METHODOLOGY AND DESIGN

3.1 Overall Trial Design

This is a prospective, single-center, open-label, non-randomized, dose escalation, comparative, safety study of IV and SC injected Tc 99m tilmanocept in the localization and detection of cutaneous and non-cutaneous KS lesions in subjects with biopsy-confirmed KS. This study includes IV administration of 3 doses Tc 99m tilmanocept: 100 μ g/ 5 mCi, 100 μ g/ 10 mCi and 200 μ g/ 5 mCi. All subjects will receive IV administration at one of these three doses. Cohort 3 will serve as a comparator arm, and Cohort 3 subjects will additionally receive a SC injection of Tc 99m tilmanocept at the Cohort 3 dose of 200 μ g/ 5 mCi. Following IV injection of Tc 99m tilmanocept, all subjects will have whole body planar imaging with optional SPECT/CT imaging beginning 60-75 minutes post-IV injection. Following SC injection of Tc 99m tilmanocept, Cohort 3 subjects will undergo whole body planar imaging with optional SPECT/CT imaging twice: first beginning 60-75 minutes after SC injection, and again 4-6 hours post-SC injection. The Schedule of Events, [Appendix 1](#), contains a list of all study procedures and time-points. Study activities are described in detail in [Section 7](#).

3.2 Justification for Study Design and Population

This study is designed to evaluate the safety and tolerability of escalating doses of IV Tc 99m tilmanocept and to compare results obtained from IV and SC administrations of Tc 99m tilmanocept in the same subjects. Whole body planar imaging will be utilized, as well as optional SPECT/CT to provide greater resolution of areas of Tc 99m tilmanocept localization.

This study is designed to evaluate the use of Tc 99m tilmanocept as an imaging agent in HIV-positive subjects with biopsy-confirmed KS by evaluating the localization in known and unknown cutaneous and non-cutaneous lesions.

No prior clinical trials have been conducted to evaluate IV administration of Tc 99m tilmanocept performance in subjects with KS. One previous clinical trial was conducted to evaluate SC administration of Tc 99m tilmanocept performance in subjects with KS. The rationale for evaluating Tc 99m tilmanocept in this subject population is discussed in [Section 1.1](#) and [Section 1.2](#).

3.3 Protocol Adherence

Strict adherence to all specifications outlined in this protocol is required for all aspects of the study conduct; the investigator may not modify or alter the procedures described in this protocol. If protocol modifications are necessary, all alterations that are not solely of an administrative nature require a formal protocol amendment for the involvement of the Institutional Review Board(s) (IRB(s)).

If an investigator has deviated from the protocol in order to eliminate an immediate hazard to subjects or for other inevitable medical reasons, the investigator shall document all such deviations, including the reasons thereof, and submit the document to the sponsor and the head of the medical institution as applicable.

3.4 Trial Duration

Subjects will be “on trial” for up to 50 days.

4 STUDY POPULATION

The evaluation of Tc 99m tilmanocept in KS will involve up to 14 enrolled, injected, and imaged subjects.

4.1 Inclusion Criteria

Each subject must meet the following criteria to be enrolled in this study.

1. The subject has provided written informed consent with HIPAA authorization before the initiation of any study related procedures.
2. The subject is at least 18 years of age at the time of consent.
3. The subject is HIV positive.
4. The subject has a biopsy-confirmed diagnosis of KS and is classified into one of the categories below:
 - a. Confirmed cutaneous KS/oral lesions without edema
 - b. Confirmed cutaneous KS/oral lesions with edema
 - c. Confirmed cutaneous KS/oral lesions with or without edema and suspected non-cutaneous KS due to clinical symptomology or confirmed non-cutaneous KS lesion(s).

4.2 Exclusion Criteria

Subjects who meet any of the following criteria will be excluded from the study.

1. The subject is pregnant or lactating.
2. The subject has received chemotherapy or radiation therapy to KS sites within six weeks of enrollment.
3. The subject has known sensitivity to dextran.
4. The subject has received an investigational product within 30 days prior to the Tc 99m tilmanocept administration on Day 1.
5. The subject has received any radiopharmaceutical within 7 days prior to the administration of Tc 99m tilmanocept on Day 1.
6. Any condition that, in the clinical judgment of the treating physician, is likely to prevent the subject from complying with any aspect of the protocol or that may put the subject at unacceptable risk.

4.3 Kaposi Sarcoma Classification

All subjects will have a biopsy-confirmed diagnosis of KS prior to screening. Subjects will be classified into 1 of 3 categories: a) confirmed cutaneous/oral lesions without edema, b) confirmed cutaneous/oral lesions with edema, or c) confirmed cutaneous/oral lesions with or without edema and suspected non-cutaneous KS due to clinical symptomology or confirmed non-cutaneous lesions.

4.4 Recruitment

Up to fourteen (14) evaluable subjects will be recruited from medical practice in accordance with the inclusion and exclusion criteria listed above. Potentially suitable subjects will be asked by the treating specialist about their willingness to participate in this trial. An assessment of safety and preliminary localization results will occur at the completion of each cohort. Up to fourteen (14) subjects will be enrolled, injected, and imaged.

4.5 Withdrawal

In accordance with the Declaration of Helsinki, each subject is free to withdraw from the trial at any time and without providing a reason.

A subject who withdraws consent prior to arrival at the study site on Day 1 will be considered a screen failure.

Should a subject withdraw after administration of the investigational product, all efforts will be made to complete and report the observations up to the time of withdrawal as thoroughly as possible.

The investigator may withdraw a subject from the trial at any time at the discretion of the investigator for any of the following reasons:

- A protocol violation occurs
- A serious or intolerable AE occurs
- A clinically significant change in a laboratory parameter occurs
- At the investigator's/sponsor's discretion as long as it is in the best interest of the subject
- The sponsor or investigator terminates the study
- The subject requests to be discontinued from the study

